6.3.12 RMD or Placebo for RMD Infusion

For correct RMD dosing calculate BSA per section 5.1. See section 6.3.4, Clinical Assessments, Study Treatment Modifications.

Cohorts 1 – 3

RMD will be administered as a single 4-hour intravenous infusion starting at entry/Hour 0. Potassium and magnesium levels will be assessed prior to infusion at the pre-entry visit (day -21 to -7). Blood potassium and magnesium values must be within normal limits. If the pre-entry potassium and/or magnesium value(s) is below the site's clinical laboratory's limit of normal, the participant should be supplemented as medically indicated, retested, and evaluated prior to study entry. If the pre-entry potassium and/or magnesium value(s) is high, the value(s) should be retested, and evaluated prior to study entry. The repeated pre-entry potassium and/or magnesium values must be within normal range for the site's limit of normal for study entry. Given blood volume constraints in this study, sites should use pediatric volume tubes whenever feasible.

Cohort 4

RMD will be administered as a 4-hour intravenous infusion at four time points, as indicated in the Cohort 4 SOE, section 6.1.3 or, as warranted, in the Cohort 4 - Delayed Infusion SOE, section 6.1.4, . See section 6.3.7 for pre-infusion safety testing.

6.3.13 ART Adherence Assessment

Participants will be asked to complete a brief ART adherence questionnaire per the SOE.

7.0 CLINICAL MANAGEMENT ISSUES

Criteria for participant management, dose interruption and discontinuation changes in drug treatment will be mandated only for toxicities attributed to RMD. Toxicities due to drugs in the antiretroviral regimen should be managed according to standard clinical practice, with the goal of maintaining continuous therapy, if possible.

The grading system for drug toxicities is located in the Division of AIDS Table for Grading the Severity of Adult and Pediatric Adverse Events, Version 1.0, December 2004 (Clarification, August 2009), which can be found on the DAIDS RSC Web site: http://rsc.tech-res.com/clinical-research-sites/safety-reporting.

NOTE: The core team must be notified within 24 hours by email at [contact] regarding toxicities thought to be associated with RMD that result in the discontinuation of the infusion.

7.1 Toxicity

7.1.1 Grade 1 or 2 Toxicity (All Cohorts)

Participants who develop a Grade 1 or 2 AE or toxicity during infusion may complete the infusion at the discretion of the site investigator, and will be followed carefully. If a participant chooses to discontinue the infusion, the site should notify the A5315 Core Team at [contact] and encourage the participant to complete safety visits for the study. Grade 1 or 2 AEs that may be related to RMD should be handled according to standard clinical practice and documented.

7.1.2 Grade 3 Toxicity

Cohorts 1 – 3

Participants who develop a Grade 3 AE or toxicity during infusion should have the infusion discontinued and the A5315 Core Team should be notified. Grade 3 AEs or toxicities that occur following infusion should be handled according to standard clinical practice and the A5315 Core Team should be notified. Participants who experience a Grade 3 AE or clinical event must return for a Week 8/Day 56 visit.

Cohort 4

Participants who develop a Grade 3 AE or toxicity during infusion should have the infusion discontinued. The A5315 Core Team should be notified within 48 hours (preferably within 24 hours). No further infusions will be performed. Refer to section 6.2.5 for required evaluations.

Grade 3 AEs or toxicities that occur following an infusion should be handled according to standard clinical practice, and the A5315 Core Team should be notified.

7.1.3 Grade 4 Toxicity

Cohorts 1 – 3

Participants who develop a Grade 4 AE or toxicity during infusion will have the infusion discontinued. Participants experiencing Grade 4 AEs should be followed closely until the resolution of the AE to < Grade 2 and the A5315 Core Team must be consulted within 72 hours (preferably within 24 hours). Participants who experience a Grade 4 AE or clinical event must return for a Week 8/Day 56 visit.

Cohort 4

Participants who develop a Grade 4 AE or toxicity during infusion should have the infusion discontinued. The A5315 Core Team should be notified within 48 hours (preferably within 24 hours). No further infusions will be performed. Refer to section 6.2.5 for required evaluations.

Grade 4 AEs or toxicities that occur following an infusion should be handled according to standard clinical practice, and the A5315 Core Team should be notified.

7.1.4 Nausea/Vomiting

Nausea/vomiting may be treated symptomatically with oral antiemetics or antiemetic suppositories per standard clinical practice.

7.1.5 Cardiac Toxicity

Refer to the A5315 MOPS for the DAIDS Toxicity Table to grade QTc prolongation.

- Grade 1: Infusion should continue without interruption, at the discretion of the site investigator.
- Grade 2: Infusion should continue without interruption, at the discretion of the site investigator. A repeat ECG should be performed at the 7 and 14 days following the infusion.
- Grade 3 and 4: The infusion should be interrupted. If the Grade 3 QTc prolongation is considered to be most likely due to concomitant illness or medication, standard management, including discontinuation of the likely causative agent, should be undertaken. A repeat ECG should be performed 7 and 14 days after the infusion.

Several treatment-emergent changes in ECGs (including T-wave and STsegment changes) have been reported in clinical studies of RMD. The clinical significance of these changes is unknown. In this study, electrolytes and ECGs are monitored at Pre-Entry and then again after each infusion. The use of strong CYP3A4 inhibitors that may increase RMD concentrations is prohibited during the study. ECG changes observed in participants may be multifactorial. Clinicians should evaluate participants with ECG changes for other possible contributing factors and address any that are identified. Sites should contact the core team ([contact]) to help determine whether additional infusions should be cancelled.

7.2 Pregnancy

If a female participant becomes pregnant during study follow-up, the site staff should request permission to contact her regarding pregnancy outcomes at the end of pregnancy. A visit 6 months following the end of pregnancy will be conducted to assess for evidence of adverse events (AEs) in the participant and infant and an outcome case report form (CRF) will be completed. Sites must collect and record information on

pregnancy complications and outcome for all pregnancies that occur during study followup and within 180 days after an infusion.

Intrapartum complications and/or pregnancy outcome will be recorded on the CRFs. Pregnancies that occur on study must be reported prospectively to The Antiretroviral Pregnancy Registry which collects information about ART exposure and adverse pregnancy outcomes. More information is available at www.apregistry.com. [contact]; [contact].

Pregnancy Outcomes

Pregnant women will be asked to provide pregnancy outcome data. The outcome and the AEs for the participant and infant will be recorded on an outcome CRF. Site staff must request permission to contact her regarding pregnancy and infant outcomes at the end of pregnancy. Pregnancy outcomes for the participant and infant will be submitted on a CRF at the end of the pregnancy.

Procedures in the Event of Contraceptive Failure

In the event of contraceptive failure, the use of an emergency contraceptive is an option. A levonorgestrel-only emergency contraceptive (ie, Plan B) is preferred to minimize the occurrence of nausea. The use of EFV with an emergency contraceptive containing both ethinyl estradiol and levonorgestrel may cause significantly increased ethinyl estradiol levels (Stocrin package insert, 2014), thereby increasing the incidence of nausea and vomiting. Combined ethinyl estradiol/levonorgestrel emergency contraceptive is, however, an acceptable option if a levonorgestrel-only emergency contraceptive is unavailable.

- 8.0 CRITERIA FOR DISCONTINUATION
- 8.1 Permanent and Premature Treatment Discontinuation
 - Grade 3 or higher drug-related toxicity (see section 7.1 Toxicity).
 - Requirement for prohibited concomitant medications (see section 5.5).
 - Request by participant to terminate treatment.
 - Clinical reasons believed to be serious or life-threatening by the physician, even if not addressed in the toxicity section of the protocol.
 - Temperature >101.5 degrees Fahrenheit during **an** infusion.
 - Development of an allergic reaction (such as difficulty breathing, wheezing, symptomatic hypotension, hives) which is thought by the site investigator to be related to the study drug.
 - Development of a symptomatic cardiac arrhythmia.

- 8.2 Premature Study Discontinuation
 - Participant does not receive any RMD or placebo.
 - Participant lacks adequate venous access.
 - In Cohort 4, participant does not receive all four infusions of RMD or placebo for RMD.
 - In Cohort 4, participant misses more than one of the 24-hour post-infusion blood collections.
 - In Cohort 4, participant does not complete the week 11 visit.
 - Pregnancy or breastfeeding.
 - Request by the participant to withdraw.
 - Request of the primary care provider if s/he thinks the study is no longer in the best interest of the participant.
 - Participant judged by the investigator to be at significant risk of failing to comply with the provisions of the protocol as to cause harm to self or seriously interfere with the validity of the study results.
 - At the discretion of the ACTG, IRB, Food and Drug Administration (FDA), NIAID, Office for Human Research Protections (OHRP), other government agency as part of their duties, investigator, or industry supporter.
- 9.0 STATISTICAL CONSIDERATIONS
- 9.1 General Design Issues

This is a dose-escalation study in which cohorts will open sequentially based on the safety of the previous cohort. Up to three dose levels of single-dose RMD (0.5 mg/m^2 , 2 mg/m², 5 mg/m²) may be assessed in the first three cohorts. Multiple doses of RMD (at 5mg/m²) may be assessed in Cohort 4 if safety is established in Cohort 3, ie, if dose-escalation criteria are met. Each cohort of 15 participants consists of 12 evaluable participants receiving RMD and 3 receiving placebo (single dose in Cohorts 1 – 3, and multiple doses in Cohort 4).

The study is double-blinded, placebo-controlled and randomized. There are three participants receiving placebo at each dose cohort. Inclusion of a placebo group in each cohort, albeit small, may help assess treatment-related events by allowing blinded assessment of events in relation to treatment. Also, the efficacy of RMD among those receiving RMD in Cohorts 1 - 3 can be compared to those of placebo participants pooled from Cohorts 1 - 3.

Accrual of the first five participants in any cohort will be limited to one participant in a 3day period.

Analyses and dissemination of study results from Cohorts 1 - 3 will commence after Cohort 3 follow-up is completed. Analyses and dissemination of Cohort 4 results will commence after Cohort 4 follow-up is completed.

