- DURATION For participants in Cohorts 1 – 3, study duration is 4 weeks. For participants in Cohort 4, study duration is a minimum of 24 weeks; study duration will be increased if any of the infusions after the first one must be delayed. The maximum study duration for Cohort 4 participants will be 48 weeks.
- SAMPLE SIZE 60 evaluable participants (approximately 15 evaluable participants in each cohort)
- POPULATIONHIV- infected adults at least 18 years of age with CD4+ counts
≥300 cells/mm³ who have suppressed viremia on a raltegravir (RAL),
dolutegravir (DTG), or efavirenz (EFV)-based regimen or, for Cohort 4,
on a RAL- or DTG-based regimen (plasma HIV-1 RNA levels
<50 copies/mL and no blips >50 copies/mL on standard commercial
assays) and, for Cohorts 1-3 only, who have ≥0.4 HIV-1 RNA copies/mL
by single-copy assay (SCA) at screening. Plasma HIV-1 RNA ≥0.4 HIV-1
RNA copies/mL by SCA is not required as part of eligibility for Cohort 4.
- REGIMEN Participants will be sequentially enrolled to cohorts and randomized 4:1 to receive RMD or placebo as shown below.
 - Cohort 1: 12 participants will receive 0.5 mg/m² RMD in 0.9% saline 3 participants will receive placebo in 0.9% saline
 - Cohort 2: 12 participants will receive 2 mg/m² RMD in 0.9% saline 3 participants will receive placebo in 0.9% saline
 - Cohort 3: 12 participants will receive 5 mg/m² RMD in 0.9% saline 3 participants will receive placebo in 0.9% saline

SCHEMA (Cont'd)

Cohort 4: 12 participants will receive a total of 20 mg/m2 RMD in 0.9% saline (5 mg/m2 RMD at each of four dosing time points) 3 participants will receive placebo in 0.9% saline (at each of four dosing time points)

Accrual of the first five participants in any cohort will be limited to one participant in a 3-day period. Participants who do not receive or who do not complete any of the scheduled infusions of study treatment (RMD or placebo) will be replaced.

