5.1 Regimens, Administration, and Duration

At entry, participants will be randomized (4:1) to receive blinded RMD or Placebo for RMD. The first fifteen study participants enrolled in Cohort 1 and received one dose of blinded RMD or Placebo for RMD by intravenous (IV) infusion over 4 hours on Day 0. Additional participants are enrolled, approximately 15 per cohort, into different cohorts as these are opened to accrual.

Participants in Cohorts 2 and 3 received one dose of blinded RMD, at increased dosages, or placebo for RMD by IV infusion over 4 hours on Day 0. Participants in Cohort 4 will receive a dose of blinded RMD or placebo for RMD by IV infusion over 4

hours on Days 0, 14, 28, and 42, for a total of four doses. Each Cohort 4 participant will receive four doses of either RMD or placebo for RMD.

After Cohort 1, Cohorts 2 and 3 were opened sequentially, based on safety outcomes as defined in section 9.0. The decisions to open these two subsequent cohorts were made after two separate reviews of available safety data by the A5315 core team and SMC.

Body Surface Area (BSA) Calculation

The dose of RMD to be administered will be calculated based on body surface area (BSA) expressed in square meters (m²), which will be determined by weight and height measurement. Measured height and weight obtained during the complete physical exam at pre-entry is to be used for calculating the BSA for the first infusion. For Cohort 4, the weight **and height recorded at the first pre-entry visit** will be used for calculating the BSA for **Step 1**. Weight recorded at Days 7, 21, and 35 and height recorded at the first pre-entry visit will be used for Cohort 4 Steps 2, 3, and 4, respectively.

The BSA should be calculated using the BSA calculator available on the FSTRF portal.

BSA (m²) = ([Height (cm) x Weight (kg)] / 3600)^{1/2}

5.1.1 Cohort 1

Upon randomization, the participant PID and SID will be provided to the site clinic for the clinic to send a prescription to the pharmacy.

o Arm 1A (RMD)

RMD intravenously (IV) over 4-hours starting at Hour 0 on Day 0. The mg dose and corresponding volume of RMD to be added to 500 mL 0.9% Sodium Chloride for Injection, USP IV bag for infusion is based on participant's BSA per Table 5.1.1-1.

OR

o Arm 1B (Placebo for Romidepsin)

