6.2.5 Discontinuation Evaluations

Evaluations for Randomized Participants Who Do Not Start Study Treatment No further evaluations are required for participants who do not initiate RMD/placebo infusion.

Cohorts 1 – 3

All CRFs must be completed and keyed for the period up to and including entry/Hour 0.

Cohort 4

All CRFs must be completed and keyed for the period up to and including Entry/Hour 0.

Premature Treatment and Study Discontinuation Evaluations Cohorts 1 – 3

Participants who receive RMD/placebo infusion but from whom blood is not collected at the 24-hour time point should remain on study for safety monitoring through Day 28.

Participants who prematurely discontinue study participation after receiving RMD/placebo or prior to the completion of RMD/placebo infusion, will have the premature study discontinuation evaluations performed per the SOE and recorded on CRFs.

Cohort 4

Participants who prematurely discontinue study treatment due to a ≥ Grade 3 AE or clinical event or for any other reason will not have any further infusions but will be followed on study/off study treatment. Participants will remain on their current step and complete the following visits: 24-hour post-infusion, 72-hour post-infusion, 7-day (1 week) post-infusion, and premature treatment/study discontinuation evaluations 4 weeks post-infusion and will then be taken off study.

Participants from whom the blood collection is not performed at more than one of the 24-hour time points after a RMD/placebo infusion will not have any further infusions but will be followed on study/off study treatment. Participants will remain on their current step and complete the following visits: 72-hour post-infusion, 7-day (1 week) post-infusion, and premature treatment/study discontinuation evaluations 4 weeks post-infusion and then will be taken off study.

Participants who prematurely discontinue study participation after receiving four RMD/placebo infusions or prior to the completion of four RMD/placebo infusions, will have the premature study discontinuation evaluations performed per the SOE and then will be taken off study. A replacement participant may be enrolled for each participant who prematurely discontinues the study, including participants who receive all four infusions but discontinue study participation prior to the week 11 visit.

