9.4.3 Accrual

Accrual and screening will be suspended when the current cohort is fully enrolled and until the cohort is evaluated. Screening will reopen for enrollment once the decision to open the next cohort is made.

Participants who do not receive study treatment or complete the pre-infusion and hour 24 blood collection will be replaced in Cohorts 1 - 3; in Cohort 4, any participant who misses an infusion, more than one of the 24-hour post-infusion blood collections, or the week 11 blood collection will be replaced. Any participant who prematurely discontinues the 4 hour study treatment infusion for reasons other than the study treatment-attributed Grade \geq 3 events will be replaced with a participant assigned to the same dose cohort and the same arm.

Expected accrual per month is 2 to 4 participants.

In the unlikely event that dose escalation to all three doses is not undertaken due to the stopping rules noted in section 9.5, the enrollment will be expanded in the lower dose cohort(s) to maintain power for efficacy comparisons. Details and implementation of the enrollment expansion plan will be discussed in consultation with the SMC.

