6.5 Period of follow-up

For Cohorts 1-3:

Per protocol Section 6.2.3, Week 4/Day 28 evaluations will serve as the study completion evaluations for participants who have maintained an HIV-1 RNA level of < 200 copies/mL by standard ultrasensitive assay at the Day 7 visit. Also, these evaluations will be the study completion evaluations for participants who did not experience a Grade \geq 3 AE or clinical event (per protocol Section 7.1).

Participants who experience a Grade \geq 3 AE or clinical event must return for a Week 8/Day 56 visit (per protocol Section 7.1.2).

Per protocol Section 6.2.4, participants with an HIV-1 RNA level of \geq 200 copies/ml at the Day 7 visit will be contacted immediately and asked to return as soon as possible (preferably within 72 hours) for a repeat HIV-1 RNA PCR. If the repeat HIV-1 RNA PCR level after Day 7 is \geq 200 copies/ml, the participant will complete both Week 4 /Day 28 and Week 8 /Day 56 visits.

For Cohort 4:

Per protocol Section 6.1, participants will be followed for 18 weeks after the 4th infusion. Note: infusions can be delayed per protocol.

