- Summaries for each outcome at each measurement time point: N, median, 25th and 75th percentiles, min, max
- Summaries for each outcome's absolute change from baseline to each measurement time point: N, median, 25th and 75th percentiles, min, max

Wilcoxon rank sum test will be used for the comparison between groups. Wilcoxon signed rank test will be used to test within-group changes for RMD group.

Time points tested for 7.14.8-7.14.10: pre-entry (-35 to -28 days), pre-entry (-14 to -3 days), 24hr post-1st-infusion, pre-4th infusion, 24hr post-4th-infusion, week 16

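### A fully dosed Cohort 4 participant who does not complete week 11 is taken off study, so the week 16 and week 24 visits, including the last chance of a post-dose qVOA, are never held

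*Protocol*

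**What the plan says.** Protocol 8.2, which concerns leaving the study and not just stopping treatment, includes this bullet: "In Cohort 4, participant does not complete the week 11 visit". Protocol 6.2.5 gives the consequence. Cohort 4 participants who leave the study early, whether before or after completing four infusions, "will have the premature study discontinuation evaluations performed per the SOE and then will be taken off study". It allows a replacement for each of them, "including participants who receive all four infusions but discontinue study participation prior to the week 11 visit".

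Protocol 9.4.3 goes further on replacement: "any participant who misses an infusion, more than one of the 24-hour post-infusion blood collections, or the week 11 blood collection will be replaced". Protocol 9.4 also states Cohort 4 replacement criteria, but week 11 is not among them.

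Full follow-up is described in the Protocol schema, where Cohort 4 "study duration is a minimum of 24 weeks", and in SAP 6.5, where "participants will be followed for 18 weeks after the 4th infusion". The Step 4 schedule (Table 6.1.3-2) places follow-up visits at weeks 8, 11, 16 and 24. The SAP's list of tested time points for outcomes 7.14.8 to 7.14.10 ends with "24hr post-4th-infusion, week 16".

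No section of either document keeps a participant who fails the week 11 criterion on study for weeks 16 and 24.

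**The concern.** The bullet joins two separate decisions. One is whether a participant without week 11 data is evaluable or should be replaced. The other is whether that participant should go on being followed. Week 11 is the first post-dose qVOA collection, so it is a reasonable evaluability criterion. That does not make it a reason to cancel later visits that the participant could attend.

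The reservoir question shows the cost. Protocol 2.2 (rationale for Cohort 4) says this cohort will address reservoir reduction, and qVOA is the assay chosen for it. If the bullet is there to protect qVOA evaluability, it works against itself: when week 11 is missed, it also cancels the one remaining post-dose collection. Late safety observation after four doses and the week 16 immunology time point go with it.

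**Working it through.** **Planned follow-up.** Protocol 5.1 gives Cohort 4 infusions over 4 "hours on Days 0, 14, 28, and 42, for a total of four doses".

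- Fourth infusion: 42 / 7 = week 6.
- Planned follow-up after it: 24 − 6 = 18 weeks, which reproduces SAP 6.5 and the R+18 final visit of the delayed schedule.
- Follow-up forgone if it ends at week 11: 24 − 11 = 13 weeks, and 13 / 18 = 72%. This is an upper limit, because 6.2.5 sets no time for the discontinuation evaluations in this situation.
- Visits forgone: weeks 16 and 24, which are 2 of the 4 post-infusion-4 follow-up visits.

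**Primary endpoints (Protocol 9.2.1), standard schedule.**

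- The safety window closes 28 days after administration: 42 + 28 = Day 70 (week 10).
- The week 11 window is 77 ± 3, that is Days 74 to 80, so the safety window has already closed.
- The primary single copy assay and cell-associated RNA endpoints end 24 hours after the fourth infusion, about Day 43.
- The rule therefore removes no primary endpoint data.

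**What the later visits hold, against the discontinuation column (Table 6.1.3-2).**

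| Measure | Week 16 | Week 24 | Discontinuation |
|---|---|---|---|
| Clinical assessment, targeted exam, hematology | yes | yes | yes |
| LFTs/chemistries | no | yes | yes |
| Real-time HIV-1 RNA | yes | no | yes |
| CD4%, immunology storage | yes | yes | yes |
| Single copy assay, PBMCs, virology storage | yes | yes | yes |
| qVOA storage | no | yes | **no** |

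**Post-dose qVOA samples per participant.** Collections are scheduled at weeks 11 and 24 only.

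- Both visits attended: 2.
- Week 11 missed, follow-up continued: 1 (week 24).
- Week 11 missed, 8.2 applied: 0.

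**Share of an arm per case, before any replacement.** RMD 1 / 12 = 8%; placebo 1 / 3 = 33%. Neither document gives a rate of missed week 11 visits, so no expected loss can be calculated.

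**Consistency of the rules.**

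- The triggers differ. In 8.2 it is not completing the visit; in 9.4.3 it is missing the blood collection; in 6.2.5 it is leaving the study before the visit.
- The consequences differ. Replacement is permitted in 6.2.5 and mandatory in 9.4.3, and 9.4 has no week 11 criterion.
- The delayed-infusion schedule (Table 6.1.4-2) has no visit named week 11. Its counterpart is R+5 (week 6 + 5 = week 11), but 8.2 does not say so.

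**The case against.** The strongest reply is that little is lost. A reader might infer that the rule throws data away. It does not: SAP 6.3 keeps every exposed participant in the safety set, and every fully dosed participant with available data in the Cohort 4 efficacy set, with no week 11 condition. A reader might also infer that all late safety and virology information disappears. The discontinuation visit supplies one more set of everything tabulated except qVOA, and expedited adverse event reporting runs six months from enrollment in Cohort 4 (Protocol 11.4.3). The SAP's planned late virology is thin in any case. Sections 7.13.1 and 7.13.2 list no time point after 24 hours post-infusion 4, further testing awaits a team decision (7.14.1, 7.14.2), and the outcome of HIV-1 RNA at or above 200 copies/mL is routed to 7.7, which tabulates only day 7 after each infusion. All of this stands, and it limits the point.

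Replacement is also provided for, so 33% is not a net loss of late control data. That reply holds in part. A replacement brings another person's data but does not restore the removed participant's late follow-up, and 9.4.3 specifies a same-arm replacement only for infusions stopped early.

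Finally, a reader might conclude that the late data are missing not at random. Illness or poor tolerability could cause a missed week 11 visit, but the documents give no evidence on why it would be missed.

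None of this supplies a reason to cancel weeks 16 and 24. The Protocol's own rule for Cohorts 1-3 points the other way: under 6.2.5, a participant who was infused but has no 24-hour blood collection stays on study for safety monitoring through Day 28.

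**Conclusion.** The point holds as a cheap improvement to secondary, exploratory and late safety data. Read together, 8.2 and 6.2.5 give up follow-up that could have been obtained: up to 13 of 18 weeks and two visits per affected participant. The specific losses are late safety follow-up, the week 16 immunology time point (SAP 7.14.8 to 7.14.10), and the week 24 qVOA as that participant's only post-dose reservoir sample.

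It is not a threat to the primary analysis, and the documents do not support presenting it as one. The 8% and 33% figures are per case, assume full arms of 12 and 3, and precede replacement. Frequency is unknown, and informative missingness is possible but not shown. The conclusion assumes that sites apply 8.2 literally. If only replacement was intended, the text still needs correcting, because nothing in it says so.

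**What to change.** - Delete the week 11 bullet from 8.2. State that a missed week 11 visit counts as missing data and as a replacement trigger only, and that scheduled follow-up continues to week 24 (R+18 on the delayed schedule).
- Reconcile 6.2.5, 9.4 and 9.4.3: use one trigger (visit or blood collection), make replacement either permitted or required throughout, and put the criterion in 9.4 if it is kept.
- State how the criterion applies on the delayed schedule, where the corresponding visit is R+5.

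The cost is a short text amendment. No new visit type or assay is needed. The one real downside is that already-scheduled visits continue for the original participant alongside those of any replacement.
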